8.2.1.3 Specific Th2 CMI response against the SARS-CoV-2 virus measured by IL-4 ELISpot

The specific Th2 CMI response on Day 0, Day 21, and Day 42 measured by IL-4 ELISpot will be compared between treatment groups and timepoints. The Wilcoxon Rank Sum Test will be used to estimate the difference in response between treatment groups, along with the corresponding 95% CI for the median and p-value.

The Wilcoxon Signed Rank Test will be used to estimate the difference in response between timepoints, along with the corresponding 95% CI for the median and p-value.

Scatter plot of the number of T cells expressing IL-4 will be created.

8.2.2 Secondary Immunogenicity Endpoints

8.2.2.1 Nab response against the SARS-CoV-2 virus

The following analyses for the Nab assay will be performed:

- GMT (Day 128 and Day 201): The point estimates and the corresponding two-sided 95 % CI by treatment group will be calculated.
- SC rate (Day 128 and Day 201): The point estimates and the corresponding two-sided 95 % CI for subjects achieving SC by treatment group will be calculated.
- GMFR: the geometric mean of the ratio of GMTs (Day 128/Day 0, Day 201/Day 0) will be calculated.

The same methodology as in section 8.2.1.1 will be used.

8.2.2.2 Specific Th1 CMI response against the SARS-CoV-2 virus measured by IFN- γ ELISpot

The specific Th1 CMI response induced on Day 201 will be analyzed according to the same methodology as in section 8.2.1.2.

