2.2.2 Secondary Endpoints

The following secondary safety and immunogenicity endpoints are for Groups 1 and Group 2.

Safety:

1. The incidences of SAEs, MAAEs, AEs leading to withdrawal, AESIs, and deaths from Day 43 to Day 201;
2. The incidences of SAEs, MAAEs, AEs leading to withdrawal, AESIs, and deaths from Day 202 to Day 386;
3. The numbers and percentages of subjects with normal and abnormal urine, hematological, and biochemical test results within three days of first (Day 0) and second (Day 21) injections.

Immunogenicity:

1. Persistence of SARS-CoV-2 Nab response will be assessed on Days 128, 201, and 386 using the following parameters: GMT, SC rate, and GMFR.
2. SARS-CoV-2-specific antibody responses will be measured on Days 0, 21, and 42 based on the total immunoglobulin G (IgG) level, and the persistence of these antibodies will be analyzed on Days 128, 201, and 386 using the following parameters: GMT, SC rate, and GMFR;
3. SARS-CoV-2-specific Th1 CMI responses will be measured on Days 201 and 386 using the IFN- γ ELISpot assay;
4. SARS-CoV-2-specific Th2 CMI responses will be measured on Days 201 and 386 using the IL-4 ELISpot assay;

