3.2 Study Design

A randomized, multicenter, observer-blinded, placebo-controlled study with Japanese male and female subjects who are seronegative for SARS-CoV-2 antibodies and negative for SARS-CoV-2 PCR test at screening.

125 subjects will be randomized 4:1 and will receive the same 3.75 μ g of MT-2766 or placebo. Subjects will receive two intramuscular (IM) injections 21 days apart on Days 0 and 21, into the deltoid region of the alternating arm (each arm will be injected once), of one of the following blinded treatments:

- ◆ Group 1: 3.75 μ g of MT-2766 in a final volume of 0.5 mL (n=100)
- ◆ Group 2: Placebo for MT-2766 3.75 μ g in a final volume of 0.5 mL (n=25)

In addition, subjects in Group 3 (n=20) will receive two IM injections of 1.875 μ g MT-2766 21 days apart on Days 0 and 21, into the deltoid region of the alternating arm (each arm will be injected once) under open-label. The study may be completed even if fewer than 20 subjects in Group 3 are enrolled.

[figure not shown]
- ◆ Group 3: 1.875 μ g of MT-2766 in a final volume of 0.25 mL (n=20)

Subjects will be screened up to 21 days in advance of the first vaccine administration and will demonstrate a satisfactory baseline medical assessment by history, general physical examination, hematological, biochemical, urinalysis and serological analysis. Although tests for SARS-CoV-2 antibodies and PCR will be performed at screening, negative subjects will be enrolled. On Day 0 and Day 21, vaccine administration will occur. Phone contacts will be made after each vaccine administration, specifically for review of the subject's safety and concomitant medication data. Visits to the study site will occur 3 days after each vaccine administration for key safety assessments, and 21 days after each vaccine administration for key safety and immunogenicity assessments.

Subjects will return to the study site on Day 128, Day 201, and Day 386 (3-month, 6-month, and 12-month safety follow-ups and immunogenicity assessments after the last vaccine administration).

In Group 1 and Group 2, the randomization code will be opened after data lock when all subjects in Groups 1 and 2 have reached Day 42. Once the study is unblinded, if the efficacy may be inadequate or unconfirmable, public vaccination will be allowed in Group 1 (3.75 μ g of MT-2766). Once the study is unblinded, public vaccination will be allowed in Group 2 (placebo group). In these cases the subject will be withdrawn from the study.

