5 ANALYSIS SET

The statistical analysis will be based on separate analysis sets, defined as follows:

Safety Analysis Set (SAS): All subjects who received at least one dose of either the MT-2766 or placebo.

Immunogenicity Intent-to-treat (ITT) Set All subjects who receive at least one dose of either the MT-2766 or placebo and who have at least 1 post-baseline Immunogenicity assessment.

Immunogenicity Per Protocol (PP) Set Immunogenicity ITT set who do not have any major protocol violations, and who received either the MT-2766 or placebo. For the Day 21 analysis, this should include the subjects who received the first vaccine dose and had Day 0 and Day 21 immunogenicity sample collections. For the Day 42 analysis, this should include the subjects who received both vaccine doses and had Day 0 and Day 42 immunogenicity sample collections. For the Day 128 analysis, this should include the subjects who received both vaccine doses and had Day 0 and Day 128 immunogenicity sample collections. For the Day 201 analysis, this should include the subjects who received both vaccine doses and had Day 0 and Day 201 immunogenicity sample collections.

All safety analyses will be performed using the SAS. The analyses of all immunogenicity endpoints will be performed using the Immunogenicity PP set as the primary analysis population, and the immunogenicity ITT set, as a secondary analysis population.

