7.1.2.2 Geometric Mean Fold Rise (GMFR)

GMFR will be defined as the geometric mean of the ratio of GMTs (Day 21/Day 0, Day 42/Day 0, Day 128/Day 0, Day 201/Day 0).

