7.1.2.4 Immunogenicity values

If antibody titers and concentrations are below the cutoff, i.e the result is of the form ‘<xx’, the value will be set to $0.5 * xx$ before performing GMT calculations. Only samples for which PBMC preparation was performed within 8 hours will be used for analysis.

“Below LOD” in IFN- γ and IL-4 data should be considered as “0”.

“NR” in IFN- γ and IL-4 data should be considered as “not reportable” results.

Value of “< 100” and “IR” in Nab data due to hemolyzed samples should be considered as “not reportable” results.

“>ULOQ” in Nab data are results above ULOQ at the maximal dilution and the “>ULOQ” value should be assigned as “64000”.

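### Nab and IgG persistence has no summary against Day 42 in the same subjects, so waning cannot be separated from a change in who was sampled

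*SAP*

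**What the plan says.** - **Endpoint.** SAP 2.2.2: "Persistence of SARS-CoV-2 Nab response will be assessed on Days 128, 201, and 386 using the following parameters: GMT, SC rate, and GMFR". The same section treats total IgG alike. SAP 10 records that the study was discontinued and that Day 386 was not measured, so Days 128 and 201 carry the endpoint.
- **Fold rise.** SAP 7.1.2.2 lists the ratios as "Day 21/Day 0, Day 42/Day 0, Day 128/Day 0, Day 201/Day 0". Every denominator is Day 0. SAP 8.2.2.1 repeats this for the later Nab visits ("GMFR: the geometric mean of the ratio of GMTs (Day 128/Day 0, Day 201/Day 0) will be calculated") and adds "The same methodology as in section 8.2.1.1 will be used". That means a per-visit ANOVA on GMT, Fisher's exact test on seroconversion, ANCOVA on change from Day 0, and per-visit plots.
- **Who is analysed.** SAP 5 has immunogenicity analyses "performed using the Immunogenicity PP set as the primary analysis population, and the immunogenicity ITT set, as a secondary analysis population". PP membership is set visit by visit: "For the Day 201 analysis, this should include the subjects who received both vaccine doses and had Day 0 and Day 201 immunogenicity sample collections". A Day 42 sample is not required. SAP 7.2 removes out-of-window samples for the visit concerned, and SAP 7.3 leaves missing titres missing, so the ITT estimates are also available-case.
- **Who leaves.** The code is opened once Groups 1 and 2 have reached Day 42. SAP 3.2 then says that "if the efficacy may be inadequate or unconfirmable, public vaccination will be allowed in Group 1", and such subjects are withdrawn. Protocol 5.5 recommends public vaccination to the placebo group without condition. Protocol 7.8 also lets a single subject ask for it before key open, and that subject is then withdrawn.
- **Pairing elsewhere.** SAP 8.2.1.2 and 8.2.1.3 treat ELISpot timepoints as paired and use the signed rank test, and 8.2.2.2 and 8.2.2.3 carry this to Day 201. Nab and IgG have no counterpart.

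**The concern.** Most readers of a persistence result will ask how much of the post-dose-2 response is left. The three planned parameters answer that poorly.

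- **GMFR.** Protocol 3.3 excludes subjects positive on N-protein ELISA or PCR at screening, and anyone previously given a COVID-19 vaccine. Most Day 0 titres are therefore probably below the cutoff, where "the value will be set to $0.5 * xx$ before performing GMT calculations". Later GMFR then largely repeats GMT.
- **Seroconversion rate.** For an undetectable baseline, SAP 7.1.2.3 asks only for a titre of at least 40. A fall from 4000 to 40 would not change a subject's status.
- **GMT.** What remains is to read the Day 42, 128 and 201 GMTs side by side. These come from overlapping but different subjects, and the planned departures fall mostly between the visits being compared.

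At stake is whether the report can describe decline in Group 1 without mixing it with a change in composition.

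**Working it through.** The documents state no decline, retention or titre SD, so there is no planned figure to reproduce.

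**1. GMFR against GMT.** If every Day 0 Nab titre is below 10 (the undetectable level in SAP 7.1.2.3) and is reported against that cutoff, each is set to 0.5 × 10 = 5. GMFR is then GMT / 5 at every visit. It adds nothing on decline.

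**2. Effect of changing composition.** Let f be the share of Day 42 subjects still sampled, and d the mean log10 Day 42 titre of stayers minus that of leavers. If all stayers have a Day 42 sample:

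apparent Day 201/Day 42 ratio = paired ratio in stayers × 10^[(1 − f)d]

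| f | d = 0 | d = 0.1 | d = 0.3 | d = 0.5 |
|---|---|---|---|---|
| 0.9 | 1.00 | 1.02 | 1.07 | 1.12 |
| 0.7 | 1.00 | 1.07 | 1.23 | 1.41 |
| 0.5 | 1.00 | 1.12 | 1.41 | 1.78 |

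A negative d gives the reciprocals. With d = 0 there is no distortion at any retention.

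**3. Illustration.** All inputs here are assumptions: true decline 4.0-fold, log10 SD 0.5 within age group, 96 subjects at Day 42, lower titres and lower retention at age 65 or over.

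The shift is (older share of all − older share of stayers) × log10(titre fold).

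| Scenario | f | Older share of stayers | Shift (log10) | Apparent decline |
|---|---|---|---|---|
| (a) 20% older, 2-fold lower, 30% v 60% retained | 0.06 + 0.48 = 0.54 | 0.06/0.54 = 0.111 | 0.089 × 0.301 = 0.0268 | 4/1.064 = 3.76 |
| (b) 40% older, 2-fold lower, 30% v 60% | 0.12 + 0.36 = 0.48 | 0.12/0.48 = 0.250 | 0.150 × 0.301 = 0.0452 | 4/1.110 = 3.61 |
| (c) 40% older, 3-fold lower, 20% v 60% | 0.08 + 0.36 = 0.44 | 0.08/0.44 = 0.182 | 0.218 × 0.477 = 0.1041 | 4/1.271 = 3.15 |

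Simulation (20,000 runs each) agrees to within 0.01. The paired ratio returns 4.0 each time, but only because the model gives stayers and leavers the same mean decline.

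**4. Either direction.** A second simulation let retention depend on the Day 42 titre itself (100 subjects, SD 0.5, SD of individual decline 0.35, log-odds slope +1 or −1 per SD, true decline 3.98-fold). At 70% retention the side-by-side GMTs show 2.97-fold if high responders stay and 5.33-fold if they leave. At 50% retention they show 2.47 and 6.43-fold. With slope 0 they show 3.96 to 3.98-fold.

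**5. Precision.** Assume within-subject correlation ρ = 0.7, n = 96 at Day 42 and m = 96f at Day 201, where the m subjects are a subset of the n.

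- Side-by-side SE = 0.5 × √(1/m + 1/n − 2ρ/n)
- Paired SE = 0.5 × √(2(1 − ρ)/m)

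For (a), m = 51.8, so the SEs are 0.0615 and 0.0538. The 95% factors 10^(1.96 SE) are 1.32 and 1.28. The formula leaves out variation in the age mix of stayers. The simulated spreads, which include it, are x/÷1.33, 1.36 and 1.40 side by side, against x/÷1.28, 1.30 and 1.31 paired.

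**The case against.** The strongest reply is that the plan makes no claim about decline from Day 42. Protocol and SAP define persistence as GMT, seroconversion rate and GMFR at the later visits, and no test contrasts Day 42 with Day 201. That stands: a useful summary is missing, and nothing planned is computed wrongly.

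Three stronger readings are tempting, and the documents do not support them.

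- **That the planned fold rise is confounded.** Within a visit it compares each subject with that subject's own Day 0, and the PP set requires the Day 0 sample. The difficulty appears only when results from different visits are compared.
- **That persistence will be overstated.** No passage says that leavers have lower titres, or that age affects titre or uptake of public vaccination. The Group 1 condition reads as a judgement on the group, not a rule on individual titres. Accepting vaccination is still each subject's choice, so selection cannot be ruled out, but its direction and size are unknown. Scenarios (a) and (b) move the ratio by factors of only 1.06 and 1.11, well inside sampling error.
- **That pairing brings a large gain in precision.** A 95% factor of about x/÷1.49–1.57 for the side-by-side comparison results only if the two visits are treated as independent samples. Later subjects are mostly also in the Day 42 sample, so the real gain is modest.

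There is also partial mitigation. SAP 8.2 lists all immunogenicity data, so paired ratios could be derived afterwards. Reverse cumulative distribution curves and scatter plots are planned for Nab, though per visit. The CMI endpoints already have paired tests.

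**Conclusion.** The point holds as a cheap improvement, limited to Nab and IgG. The plan gives no same-subject comparison with Day 42, and its available-case sets can change between Day 42 and the later visits, so a side-by-side reading cannot separate waning from composition.

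If leaving is unrelated to titre there is no bias, only some loss of precision. If it is related, the apparent decline can be too small or too large. The range of 3.1 to 3.8-fold for a true 4.0-fold decline, and the narrowing from x/÷1.33–1.40 to x/÷1.28–1.31, rest on assumed decline, SD, sample size, age mix, titre difference, retention and correlation. They show what is possible, not what happened.

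The weight is moderate at most: this is a descriptive secondary endpoint in a discontinued study whose size was not based on power (SAP 3.4).

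**What to change.** In SAP 7.1.2.2, 8.2.2.1 and 8.2.2.4 add for Group 1, in PP subjects with both samples:

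- **Nab:** within-subject geometric mean ratios Day 128/Day 42 and Day 201/Day 42, each with a 95% CI from a paired t interval on log10 titres.
- **IgG:** the same for Day 201/Day 42. Add Day 128/Day 42 only if those samples were assayed. SAP 8.2.2.4 plans no Day 128 IgG analysis, while 7.1.2.3 and 9.3 include that visit and SAP 10 says that some items were not measured.
- **Display:** the Day 42 GMT of those same subjects beside each later GMT.
- **Reporting rule:** base any statement on decline on these ratios.

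State three limits with the table. The ratio describes only subjects still sampled. It does not recover decline in leavers if theirs differs. It understates decline if Day 42 Nab values sit at 64000, the value that SAP 7.1.2.4 assigns above the upper limit of quantification.

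The cost is a few lines of SAP text and one table from titres already collected.

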8.2.2.3 Specific Th2 CMI response against the SARS-CoV-2 virus measured by IL-4 ELISpot

The specific Th2 CMI response induced on Day 201 will be analyzed according to the same methodology as in section 8.2.1.3.

8.2.2.4 Specific antibody response against the SARS-CoV-2 virus by the total IgG levels

The GMT will be calculated on Day 0, Day 21, Day 42 and Day 201 as well as the GMFR (Day 21/Day 0, Day 42/Day 0, Day 201/Day 0). SC rate will be calculated on Day 21, Day 42 and Day 201.

GMT will be compared between treatment groups using the analysis of variance (ANOVA) model.

For SC rate, Fisher's exact test will be used to compare between the treatment groups, along with exact Clopper-Pearson 95% CI.

GMFR will be compared using the ANCOVA model. The GMFR will be derived by using ANCOVA to model the difference in the log of the titer values between Day 21 and Day 0, between Day 42 and Day 0, between Day 201 and Day 0 with treatment group as main effect and log-transformed baseline titer as covariate.

The RCD curve will be plotted.

8.2.3 Specific CMI response against the SARS-CoV-2 virus measured by the percentage of CD4+ T cells expressing functional markers

The CMI response on Day 0, Day 21 and Day 42 measured by the percentage of T cells expressing functional markers, using flow cytometry will be compared between treatment groups and timepoints. The Wilcoxon Rank Sum Test will be used to estimate the difference in response between treatment groups, along with the corresponding 95% CI for the median.

The Wilcoxon Signed Rank Test will be used to estimate the difference in response between timepoints, along with the corresponding 95% CI for the median.

Parameters
CD4+CD8- > IL2+ percent of CD4, CD4+CD8- > IL4+ percent of CD4, CD154+ > IFN_TNF_IL2_Poly percent of CD4, CD4+CD8- > IFN_TNF_IL2_Poly percent of CD4

8.2.3.1 Specific antibody response against plant glycans measured by serum IgE levels

The specific antibody response against plant glycans induced on Day 0, Day 42 and Day 201 will be analyzed by evaluating the percentage of subjects with detectable IgE levels at each timepoint for each treatment group and the percentage of subjects with undetectable IgE levels at each timepoint for each treatment group along with corresponding two-sided 95% exact (Clopper-Pearson method). The difference in percentage between Day 42 and Day 0, Day 201 and Day 0 and associated 95% CI for the difference will be calculated for each treatment group.

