12.1.4.1.2 Hypersensitivity Reactions

All reported events will also be monitored for hypersensitivity reactions after exposure to the CoVLP formulation. Severe allergic reactions are considered to be an important potential risk (based on the theoretical risk that using plants for the production of biotherapeutics may induce hypersensitivity), Medicago will require that supervision are available to manage any possible anaphylactic reactions in this study. To collect data on these events, Medicago will closely monitor and assess allergic reactions assessed as related to the investigational product as AESIs.

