14.4.4 Analysis of Exploratory Endpoints

Immunogenicity:

For Group 1 and Group 2, the CMI response induced on Day 0, Day 21, Day 42, Day 201, and Day 386 will be measured by the percentage of CD4+ T cells expressing functional markers, using flow cytometry (ICS), for each treatment group. The responses will be compared between treatment groups and timepoints using appropriate non-parametric (Wilcoxon) models. Additional details will be provided in the SAP.

For Group 1 and Group 2, the specific antibody response against plant glycans induced on Day 0, Day 42, Day 201 and Day 386, will be analyzed by evaluating the percentage of subjects with detectable IgE levels at each timepoint for each treatment group and the percentage of subjects with IgE levels, relative to baseline (Day 0), that are greater than the limit of detection at Day 42, Day 201, and Day 386 for each treatment group. Additional details will be provided in the SAP.

For Group 3, the same analyses as the primary and secondary endpoints in Groups 1 and Group 2 will be performed.

Safety:

For Group 3, the same analyses as the primary and secondary endpoints in Groups 1 and Group 2 will be performed.

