1 INTRODUCTION

This statistical analysis plan (SAP) is based on the final protocol (v3.0) dated 16-NOV-2021. The plan covers statistical analysis, tabulations and listings of the study data to assess the safety and immunogenicity of MT-2766.

Any statistical analysis details described in this document supersede any description of statistical analysis in the protocol.

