2.2.3 Exploratory Endpoints

Immunogenicity:

1. For Group 1 and Group 2, SARS-CoV-2-specific CMI responses will be assessed on Days 0, 21, 42, 201, and 386 based on the percentage of CD4+ T cells expressing functional markers.
2. For Group 1 and Group 2, plant glycan-specific antibody responses will be assessed on Days 0, 42, 201 and 386 based on serum IgE levels directed against bromelain-derived cross-reactive carbohydrate determinant MUXF3.
3. For Group 1 and Group 2, Further characterization of the MT-2766-induced immune response, if informative;
4. For Group 3 (1.875 μ g of MT-2766), the same analyses as the primary and secondary endpoints in Groups 1 and Group 2 will be performed as exploratory endpoints.

Safety

1. For Group 3, the same analyses as the primary and secondary endpoints in Groups 1 and Group 2 will be performed as exploratory endpoints.

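### SAP 8.2.3.1 summarises plant-glycan IgE only as detectable or undetectable, so a rise in subjects already detectable at Day 0 would be visible only in the data listings

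*SAP*

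**What the plan says.** SAP 2.2.3 defines the endpoint as a response "based on serum IgE levels directed against bromelain-derived cross-reactive carbohydrate determinant MUXF3", assessed in Groups 1 and 2. SAP 8.2.3.1 plans three things:

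- "evaluating the percentage of subjects with detectable IgE levels at each timepoint for each treatment group";
- "the percentage of subjects with undetectable IgE levels at each timepoint for each treatment group", with exact 95% limits;
- "The difference in percentage between Day 42 and Day 0, Day 201 and Day 0 and associated 95% CI for the difference", within each arm.

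It plans no geometric mean, fold change, shift table, result by Day 0 status or between-arm comparison for IgE.

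Protocol 14.4.4 has the same first measure. Its second is different: "the percentage of subjects with IgE levels, relative to baseline (Day 0), that are greater than the limit of detection" at the later visits. The SAP puts the percentage undetectable in its place and states in section 1 that "Any statistical analysis details described in this document supersede any description of statistical analysis in the protocol". SAP section 10, which records changes from the protocol, mentions that Group 3 was not enrolled and that the study was discontinued. It does not mention this change.

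SAP 8.2 says that all immunogenicity data will be listed.

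**The concern.** Every other immunogenicity assay in the SAP is analysed on its own scale: Nab and IgG by geometric mean and fold rise, ELISpot and CD4+ responses by Wilcoxon methods. The seroconversion rule in SAP 7.1.2.3 gives subjects detectable at Day 0 a separate criterion, a fourfold rise, because detectability cannot register a response in them. IgE has no such provision. The SAP's log10 transform (7.1.2.1) and its half-cutoff rule for results where "If antibody titers and concentrations are below the cutoff" (7.1.2.4) are not applied to it in 8.2.3.1.

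The protocol (12.1.4.1.2) treats severe allergic reaction as an important potential risk, "based on the theoretical risk that using plants for the production of biotherapeutics may induce hypersensitivity", and this is the laboratory assay aimed at that mechanism. The eligibility criteria exclude documented anaphylaxis to plants and serious allergy to vaccine constituents, but not pre-existing plant-glycan IgE. Subjects detectable at Day 0 can therefore enrol. A boost of their existing IgE would be tabulated as no change.

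**Working it through.** The documents give no figure for this endpoint (no baseline rate, detection limit, effect size or power), so there is nothing to reproduce. From the documents: 100 vaccine and 25 placebo subjects (SAP 3.2), exact limits (8.2.3.1), half-cutoff imputation (7.1.2.4) and two-sided 0.05 (6.2). Everything else below is assumed.

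**1. The second percentage adds nothing.** Percentage undetectable = 100 − percentage detectable.

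**2. Response of the planned statistics to a rise in baseline-detectable subjects, without assay error.** Let a share p be detectable at Day 0 and let their IgE rise by a factor f, with no change in the others. Detectable at Day 42 = np, detectable at Day 0 = np, difference = 0 for any f ≥ 1. This was checked for p = 5, 10, 20 and 30%, f = 1, 2, 4 and 10, and n = 100 and 25. The difference was exactly 0 in every case.

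**3. What a level summary shows in the same data.** Undetectable subjects take half the cutoff at both visits, so their ratio is 1. The overall geometric mean fold rise is f^p.

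| n = 100, f = 10 | Detectable Day 0 → Day 42 | Overall fold rise |
|---|---|---|
| p = 5% | 5% → 5% | 10^0.05 = 1.12 |
| p = 10% | 10% → 10% (95% CI 4.9–17.6% at both) | 10^0.10 = 1.26 |
| p = 20% | 20% → 20% | 10^0.20 = 1.58 |
| p = 30% | 30% → 30% | 10^0.30 = 2.00 |

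**4. With assay error.** Simulation: log10 IgE normal with total SD 0.6, mean set to give p, and within-subject SD 0.10 per visit. A doubling confined to baseline-detectable subjects moves the percentage detectable by 1.6 to 3.3 points for p = 10 to 30%. That movement comes only from noise at the cutoff and does not measure the rise.

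**5. What tests on the level could detect.** Same doubling; signed-rank within the vaccine arm, rank-sum on log10 change between arms (100 vs 25).

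| p | Within-subject SD | Signed-rank power | Rank-sum power |
|---|---|---|---|
| 10% | 0.10 | about 97% | about 31% |
| 10% | 0.30 | about 33% | about 8% |
| 5% | 0.10 | 52% | 15% |
| 2% | 0.10 | 3% | 6% |

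With no effect, these tests reject in about 6% of trials or fewer.

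**6. Bias in the obvious subgroup estimate.** Selecting subjects by a noisy Day 0 value above the cutoff, then imputing half the cutoff for those who fall below it later, pulls their fold change down. With no true effect it averages 0.85–0.91 at SD 0.10 and 0.54–0.66 at SD 0.30. At SD 0.30 a true doubling reads as 1.10–1.33. The all-subject fold change involves no such selection.

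**The case against.** Four points have weight.

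- **The data are not hidden.** SAP 8.2 lists all immunogenicity data, so a reader who infers that such a rise cannot appear in any planned result goes too far. This stands: the gap is in summaries and estimates. The default descriptive summary in SAP 6.1 does not close it, because it yields where something else is specified, and 8.2.3.1 specifies something else.
- **The endpoint is exploratory, in a study without a power basis, and detectability is also the protocol's measure.** This stands and limits the weight of the point.
- **Hypersensitivity is assessed clinically.** It is an AESI within the primary safety endpoints, identified by broad and narrow SMQ terms. A reader might infer that the risk goes unmonitored; the documents do not support that. Blood immunoglobulin E increased is on the Appendix 3 list, but it counts only if reported as an adverse event.
- **Power contrasts can mislead.** It is tempting to say that the current plan has almost no power. The SAP plans no test for IgE, so it has no power to quote. The figures above describe the added analysis only, and they fall steeply as within-subject SD rises or the detectable share drops.

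Nor can one say that the protocol's second measure would have caught these rises. Read as a change from Day 0 exceeding the detection limit, it would catch some; read as newly detectable, none.

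**Conclusion.** The point holds as a cheap improvement to an exploratory analysis. The planned IgE summaries are binary, one is the complement of another, and none measures a rise in subjects already detectable at Day 0. The result of exactly 0 in step 2 needs no distributional assumption beyond absence of assay error; with error, the percentage moves a few points for an incidental reason.

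How much this matters in practice is unknown. It depends on the share detectable at Day 0 and on within-subject variability over six weeks to six months. Under the assumptions shown, a within-arm test on the level ranges from highly informative (about 97%) to uninformative (3%), and the between-arm test is weak at 10% detectable or fewer (31% at best).

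Separately, and without any assumption, the SAP replaced a protocol measure without recording the change in section 10.

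**What to change.** In SAP 8.2.3.1:

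1. Add the geometric mean IgE level by arm at Days 0, 42 and 201, and the within-subject fold change from Day 0 with 95% CI in all subjects, using the log10 transform of 7.1.2.1 and the half-cutoff rule of 7.1.2.4.
2. Compare log10 change between arms with the rank-sum test already used for the CMI endpoints.
3. Keep the detectable percentages.
4. Show subjects detectable at Day 0 descriptively only, vaccine beside placebo. Do not report a one-arm fold change for them, given the downward bias in step 6.
5. Either define the protocol's baseline-referenced measure unambiguously and restore it, or record its removal in section 10.

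The cost is one extra table and a few lines of text, with no new samples or assays. Protocol 14.5 allows the change before lock, documented in the SAP and study report, or after lock as a distinguished additional analysis.

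The downside is imprecision. At 10% detectable, about 25 × 0.10 = 2.5 placebo subjects would be detectable at Day 0. Day 201 numbers will be smaller if placebo subjects leave for public vaccination after unblinding.

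### SAP 8.2.3.1 tabulates only the net change in plant-glycan IgE detectability, where Protocol 14.4.4 plans a subject-level measure relative to Day 0 (minor)

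*SAP*

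**What the plan says.** The endpoint is exploratory. SAP 2.2.3 states that "plant glycan-specific antibody responses will be assessed on Days 0, 42, 201 and 386 based on serum IgE levels", for Groups 1 and 2.

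Protocol 14.4.4 gives two analyses. The first is "evaluating the percentage of subjects with detectable IgE levels at each timepoint for each treatment group". The second is "the percentage of subjects with IgE levels, relative to baseline (Day 0), that are greater than the limit of detection at Day 42", continuing to Days 201 and 386. It leaves further detail to the SAP.

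SAP 8.2.3.1 has three elements:
- the percentage detectable at each visit;
- "the percentage of subjects with undetectable IgE levels at each timepoint for each treatment group", both percentages "along with corresponding two-sided 95% exact (Clopper-Pearson method" interval;
- a change over time, separately by arm: "The difference in percentage between Day 42 and Day 0, Day 201 and Day 0 and associated 95% CI for the difference will be calculated".

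It has no count of subjects who move from undetectable to detectable, no shift table, and no interval method for the difference.

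SAP Section 1 says that SAP analysis details supersede the protocol. SAP Section 10 lists as changes only that Group 3 was not enrolled and that Day 386 and some other items were not measured. Protocol 14.5 asks that an amendment made before data lock, and its reason, be described in the SAP.

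**The concern.** The question behind the assay is whether vaccination induces IgE to plant glycans in a subject who had none. The protocol gives the context in 12.1.4.1.2, which refers to the "theoretical risk that using plants for the production of biotherapeutics may induce hypersensitivity". The second protocol measure is tied to each subject's own Day 0 value. The SAP's difference compares two group percentages, so a subject who becomes detectable is offset by one who stops being detectable. A reader of the final tables could see little or no change and have no table showing how many subjects newly became detectable.

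The replacement is also unannounced. Discontinuation of the study does not explain it, because Day 42 and Day 201 IgE both remain in SAP 8.2.3.1.

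**Working it through.** The documents state no IgE rate, effect size or power for this endpoint, so there is no planned figure to reproduce. Group sizes of 100 and 25 are from SAP 3.2. Every baseline rate, gain and loss below is an assumption chosen to show the range.

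**1. What the SAP difference measures.** Take n subjects tested at both visits. Let b be the number going from undetectable to detectable, and c the number going the other way.

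- SAP difference = (b − c)/n
- Newly detectable = b/n, or b divided by the number undetectable at Day 0

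The two agree, with n as denominator, only when c = 0.

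**2. Size under assumed counts.** The interval for the difference is paired Wald, (b − c)/n ± 1.96 × √(b + c − (b − c)²/n)/n. The interval for b/n is Clopper-Pearson.

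| Arm (detectable at Day 0) | b | c | SAP difference, points (95% CI) | Newly detectable, b/n (95% CI) |
|---|---|---|---|---|
| n = 100 (20) | 5 | 0 | +5.0 (0.7 to 9.3) | 5.0% (1.6 to 11.3) |
| n = 100 (20) | 5 | 3 | +2.0 (−3.5 to 7.5) | 5.0% (1.6 to 11.3) |
| n = 100 (20) | 5 | 5 | 0.0 (−6.2 to 6.2) | 5.0% (1.6 to 11.3) |
| n = 100 (20) | 8 | 8 | 0.0 (−7.8 to 7.8) | 8.0% (3.5 to 15.2) |
| n = 25 (5) | 2 | 2 | 0.0 (−15.7 to 15.7) | 8.0% (1.0 to 26.0) |

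The assumed Day 0 rate does not enter the difference or b/n. It changes only the rate among those undetectable at Day 0: 5/80 = 6.25% (2.1 to 14.0) with 20 detectable, and 5/90 = 5.6% (1.8 to 12.5) with 10 detectable.

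**3. Untested subjects.** SAP 6.1 makes the default denominator all N subjects in the group and analysis set, and SAP 7.3 leaves missing immunogenicity data missing. If m subjects detectable at Day 0 have no later result, the difference becomes (b − c − m)/N. With N = 100, b = 5, c = 0 and m = 2, it is +3.0 points although five subjects are newly detectable. This bears mainly on the ITT set, since the PP set for each visit requires a Day 0 sample and a sample at that visit.

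**4. The interval method matters.** Take the first row, where the percentage goes from 20% to 25%. The paired interval is 0.7 to 9.3. Treating the visits as independent gives 5.0 ± 1.96 × √(0.20 × 0.80/100 + 0.25 × 0.75/100) = 5.0 ± 11.6, or −6.6 to 16.6. One excludes zero and the other does not, and SAP 8.2.3.1 does not say which kind applies.

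**5. The undetectable row.** With every subject tested it mirrors the detectable row: 10/100 gives 4.9% to 17.6%, and 90/100 gives 82.4% to 95.1%. Under the SAP 6.1 denominator with missing samples, the two rows need not add to 100%, so the second can separate negative from untested.

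**The case against.** The protocol clause is loose. It could mean newly detectable, or a rise from Day 0 larger than the limit of detection, and it sets no at-risk denominator. Since detail is left to the SAP, the visit-to-visit difference may be the SAP's attempt to make the clause operational. That stands in part: the SAP keeps a comparison with baseline, at group level. But both readings of the clause are subject-level, and neither can be recovered from the SAP's summaries.

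Cancellation needs subjects who lose detectability, and nothing in the documents says how many there would be. Equal gains and losses are also what fluctuation around an assay limit produces, and a newly detectable percentage on its own would then count noise. This stands, and it is why losses and the placebo arm must be shown beside the gains.

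The consequence is limited. The endpoint is exploratory in a study without a power calculation. SAP 8.2 lists all immunogenicity data, so individual cases can be found by hand. Clinical hypersensitivity is analysed separately as an adverse event of special interest (SAP 7.1.3.1.3 and 8.3.2). All of this stands and sets the priority.

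A reader might infer three stronger things that the documents do not support:
- That the undetectable row is pure duplication and should go. This holds only when everyone is tested.
- That the SAP would hide actual sensitisation by the vaccine. The documents contain no IgE data, and a balanced table does not distinguish sensitisation from assay noise.
- That a fold change is owed for subjects already detectable at Day 0. Protocol 14.4.4 plans percentages only, and if its clause means newly detectable, it would miss such rises too.

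**Conclusion.** The point holds as a minor one. SAP 8.2.3.1 omits the subject-level IgE measure that Protocol 14.4.4 plans. What it offers instead is a net change with an unspecified interval method, and Section 10 does not record the departure.

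The tables understate new detectability by c/n when everyone is tested at both visits, and by (c + m)/N under the default denominator when some subjects detectable at Day 0 are untested later. That amount is zero if nobody loses detectability and all are tested. It is 5 points in the assumed case of 5 gains and 5 losses among 100. The documents do not allow it to be estimated. No primary conclusion and no clinical hypersensitivity analysis depends on it.

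**What to change.** In SAP 8.2.3.1:

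1. Add, by arm, a table of Day 0 status (detectable or undetectable) against Day 42 status, and the same against Day 201, among subjects tested at both visits.
2. From it, report the number and percentage newly detectable with a Clopper-Pearson 95% interval and a stated denominator. Show MT-2766 and placebo side by side, with the number losing detectability, so that assay fluctuation can be judged.
3. Name a paired-proportion interval for the visit-to-visit difference.
4. Define what *relative to baseline* means for this assay.
5. Record any remaining departure from Protocol 14.4.4 in SAP Section 10.

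The undetectable row may stay, and no fold-change analysis is needed. The cost is a few lines of SAP text and one small table from data already collected, with no new samples.
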